7. STUDY TREATMENTS

7.1 Study Infusion Continuation and Halt Guidelines

Procedure-related cardiac arrhythmias will be handled according to current 2004 ACC/AHA/ESC practice guidelines for management of subjects with ventricular arrhythmias and the prevention of sudden cardiac death will be implemented.

After approximately 50% of the intracoronary infusion of investigational agent has been completed, an angiographic determination of coronary flow will be performed. The following guidelines will be used to determine if the remaining investigational agent should be infused:

1. The study infusion should be continued if either TIMI 2 or TIMI 3 flow is present in the absence of ALL of the following:
2. Sustained hypotension not responsive to fluid administration;
3. Clinical signs/symptoms indicating an acute cerebrovascular event;
4. Re-elevation of ST-segments if previously resolved with PCI;
5. Onset of the patient's symptoms of myocardial ischemia unresponsive to appropriate interventions;
6. Two episodes of sustained ventricular tachycardia (VT)/ventricular fibrillation (VF) requiring cardioversion (infusion can continue if a single episode of sustained VT/VF requiring cardioversion occurred).

If TIMI flow is 1 or 0 at this assessment, regardless of associated symptoms listed above, the infusion of investigational agent must be terminated.

7.2 Definition of Adverse Event of TIMI 1 or 0 flow

If the study infusion procedure is terminated due to a TIMI 1 or 0 flow in the absence of clinically evident symptoms, this must be reported as an AE. The appropriate term to record in the CRF is 'Cardiac procedure complication'.

7.3 Investigational Agent

7.3.1 Investigational Agent Labeling

The content of the coded treatment cryovials (MPC and saline placebo) will not be known to the participating centers, subject representatives of the Sponsor, or data management organization, and the code will not be broken until after the database of the study has been locked by the CRO.

7.3.4 Investigational Agent/Control Agent Handling and Accountability

All study product accountability records including records of randomization assignment will be maintained by the investigator or qualified designee, stored in a secure location and reviewed during monitoring visits by the assigned CRA/monitor.

A horizontal bar chart consisting of five solid black bars of increasing length. The bars are positioned side-by-side, with the longest bar on the far right and the shortest bar on the far left. The chart is set against a white background with no grid lines or other markings.

7.4 Control Agent

7.4.1 Description of Control Agent

The control placebo agent is sterile saline. In addition to the coded MPC agent, the coded study placebo agent will also be provided by the Sponsor and prepared in similar volume and similar

cryovials, as applicable, as the MPC product so as to help make it as indistinguishable from the investigational MPC product as best as possible.

7.5 Blinding and Randomization

This is a double blinded study. Each subject will be blinded to his/her assigned treatment. Study blinding will be maintained as described below.

Blinded Study Personnel and Participants

Subjects, Site personnel, Investigators will remain blinded until after all safety follow-up is completed. The DSMB may choose to be unblinded.

Unblinded Study Personnel

Pre-specified unblinded clinical operations and biometrics team members at both the vendor and sponsor will have access to the unblinded efficacy results.

These pre-specified unblinded team members will be identified prior to the analysis being conducted and they will not have any operational responsibility for the conduct of the study.

An independent unblinded statistician from the CRO will support the DSMB by providing Open and Closed Reports to the DSMB independent statistician based on the best available data and other information to the DSMB.

Subjects that are admitted within a maximum of 12 hours after onset of ischemic cardiac symptoms who are experiencing a *de novo* anterior MI and qualify based on inclusion/exclusion criteria will be approached for enrollment. Eligible subjects will be randomized to receive one of three possible intracoronary treatments: Investigational product at 12.5 M or 25.0 M allogeneic MPCs or saline placebo control.

Randomization will occur after informed consent has been obtained and the PCI with stenting of the culprit LAD coronary artery lesion has been successfully completed (residual TIMI Flow Grade 3 or 2, residual diameter stenosis <20% by QCA, uncomplicated primary PCI).

The randomization and treatment assignment will be obtained from an IVRS/ IWRS.

The following stratification for duration of cardiac ischemia will be performed to ensure balanced randomization across the treatment groups:

- ≤ 2 hours
- >2 hours to ≤ 6 hours
- >6 to ≤ 12 hours.

After randomization has been performed, each subject will receive a unique identification number that will include site and subject identifiers.

7.5.1 Un-blinding Procedure

The study blind should not be broken except in a medical emergency (where knowledge of the test material received would affect the treatment of the emergency) for regulatory requirement (e.g., suspected unexpected serious adverse reactions (SUSARs)), and for the unblinded analysis of efficacy and preliminary safety once all subjects have completed the 6-month visit. If an emergency un-blinding becomes necessary, the investigator should notify the Sponsor or Medical Monitor, as soon as possible.

7.5.2 Concomitant Therapy

All subjects will receive standard post-therapy care guided by standard practices at the study center. In the event of procedure-related cardiac arrhythmias, current ACC/AHA/ESC practice guidelines for management of subjects with ventricular arrhythmias and the prevention of sudden cardiac death will be implemented. All other investigational agents or therapies are prohibited for the duration of this study.

All concomitant medications administered to study subjects will be recorded on the eCRF.

8. ASSESSMENT OF EFFICACY

Feasibility of the infusion of the investigational agent will be monitored by measurement of TIMI flow and perfusion prior to, during, and following the investigational agent infusion after successful PCI and stenting.

8.1 Primary Efficacy Endpoint

The primary efficacy endpoint is the change in LVESV as assessed by cardiac MRI from baseline to 6 months post investigational agent infusion for each MPC treatment group compared with control.

8.2 Secondary Efficacy Endpoints

- The change in LVESV as assessed by 2D-echocardiography from baseline to 6 months post investigational agent infusion.
- The change in relative infarct size as assessed by late contrast enhancement MRI (% infarct volume/total LV tissue volume) from baseline to 6 months post investigational agent infusion.
- Additional functional efficacy endpoints will be assessed with the following diagnostic studies:
 - Cardiac MRI at 2-4 days, 30 days and at Month 6.
 - LVEF
 - LVESV
 - LVEDV
 - Left ventricular wall thickness and thickening in all segments including infarct area
 - Regional wall motion score
 - Myocardial MVO measured as reduced signal intensity in the region of interest
 - MI size measured in the region of interest as late contrast enhancement
 - Myocardial salvage index
 - 2D echocardiogram at 2-4 days, 30 days and at Month 6.
 - LVEF
 - LVESV
 - LVEDV
 - Cardiac dimensions (LVESD/ LVEDD)
 - Regional wall motion score index
 - If neither MPC arm is found to be better than the placebo arm and there is no difference between the MPC groups (using the ANCOVA test with alpha=.1) in the effect on LVESV then the pooled MPC group will be compared to the placebo group for all functional parameters.
 - A subset analysis that corresponds to the stratification used during randomization will be performed. Stratification will be based on the following following categories defined as time from onset of AMI symptoms to PCI:
 - ≤ 2 hours
 - > 2 hours to ≤ 6 hours
 - > 6 to ≤ 12 hours.

- In addition, a subset analysis will be evaluated at the following ischemia duration time points:
 - ≤ 6 hours
 - > 6 to ≤ 12 hours.
- NT-Pro-BNP serum levels (as measurement biomarker for heart failure) at baseline, days 2-4 and 30 and months 3 6, 12 and 24
- Score changes for TIMI Myocardial Flow Grade and Perfusion assessments at the following day 0 time points:
 - pre-PCI,
 - immediately post-PCI,
 - after approximately 50% of intracoronary infusion of investigational agent,
 - at completion of intracoronary infusion of investigational agent.

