4.2 Secondary Objectives

- To explore a dose-response effect of intracoronary delivered MPC in the treatment of subjects with an anterior wall STEMI on LV remodelling, microvascular obstruction, and the relationship between time from onset of ischemic symptoms to primary PCI.
- To determine the effect of intracoronary delivery of allogeneic immunoselected, bone marrow-derived MPC on infarct size reduction in the treatment of subjects with STEMI undergoing primary PCI of the LAD coronary artery.

[REDACTED]

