11.2 Statistical Methods

The primary efficacy analysis will use an ANCOVA model with baseline LVESV as covariate and alpha=0.05 to test for a difference of change in LVESV from baseline to Month 6 between each MPC arm separately and the placebo arm. If neither MPC arm is found to be better than the placebo arm and there is no difference between the MPC groups (using the ANCOVA test with alpha= 0.1) in the effect on LVESV, then the pooled MPC group will be compared to the placebo group for all functional parameters.

All other statistical tests will be considered to be exploratory (post-hoc) unless a pre-specified hypothesis exists in the statistical analysis plan (SAP), which will be finalized prior to any analysis. All statistical tests will be two-sided and statistical significance will be assessed with

respect to a nominal p-value ≤ 0.05 . Any deviations from the planned analyses will be documented and justified in the final clinical/statistical study report.

The primary efficacy analysis for LVESV will be performed using cMRI collected data. The secondary efficacy analyses for LVESV will be performed using ECHO data alone, as well as ECHO data as a substitute for missing cMRI data at baseline and/or at Month 6.

In the latter case, a regression equation will be determined between measurements for LVESV-cMRI and LVESV-ECHO over a range of values. Whenever appropriate and based on LVESV-ECHO values generated using the regression equation, a LVESV-ECHO “corrected” value will be determined and used as a replacement for missing value for LVESV-cMRI.

When all enrolled subjects have completed the study through Visit 9 (Month 6), an unblinded analysis of the safety and primary and secondary efficacy endpoints will be conducted.

The primary and secondary efficacy analyses will be performed using data collected through Visit 9 (Month 6). In addition, safety analyses will be performed on all available data through Visit 12 (Month 24) at the time of conduct of the efficacy analysis. In addition, the final safety analysis will be performed at 24 months for all patients.

No additional efficacy data will be collected beyond Visit 9 (Month 6) except for cardiac biomarkers.

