11.8 Efficacy and Feasibility Analyses

Where appropriate, 95% confidence intervals for treatment differences in key feasibility measures will be constructed. Analysis of covariance (ANCOVA) may be used where appropriate to adjust for baseline differences in key continuous feasibility outcome measures and also take the site and the time from onset of AMI symptoms to PCI as covariates in the ANCOVA model. For non-normally distributed measures, the Wilcox-Mann-Whitney test or analysis of variance ANOVA of rank transformed data may be used as an alternative. For categorical measures, relative risks and nominal 95% confidence intervals will be constructed to assess strength of association. The Cochran-Mantel-Haeszel test (CMH) controlled by site and the time from the onset of AMI symptom to PCI will be used for the treatment differences. The primary feasibility analysis will be performed on the FA population, and confirmatory based on PP population.

The primary and secondary efficacy analyses will be performed on ITT, FA, and PP populations. Analysis of clinical endpoints will be performed on all analysis populations.

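### The ischemia-time question rests on subset analyses in two overlapping groupings, with no treatment-by-ischemia-time interaction planned

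*Combined protocol and SAP*

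**What the plan says.** Section 4.2 (and the synopsis, section 1.5) lists among the matters to be explored "the relationship between time from onset of ischemic symptoms to primary PCI". Randomization is stratified on ischemia duration in three bands: up to 2 hours, over 2 to 6 hours, and over 6 to 12 hours.

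Section 8.2 plans two analyses by ischemia time:

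- "A subset analysis that corresponds to the stratification used during randomization will be performed", using the three bands.
- "In addition, a subset analysis will be evaluated at the following ischemia duration time points", using up to 6 hours and over 6 to 12 hours.

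Neither item names an endpoint, a model, a comparison or a test.

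Section 11.2 gives the primary LVESV ANCOVA with baseline LVESV as covariate and compares "between each MPC arm separately and the placebo arm". It then sets a general rule. "All statistical tests will be two-sided and statistical significance will be assessed with" is completed by "respect to a nominal p-value ≤ 0.05", and no multiplicity adjustment is stated. The same section limits the standing of everything beyond the primary analysis: "All other statistical tests will be considered to be exploratory (post-hoc) unless a pre-specified hypothesis exists in the statistical analysis plan (SAP"). That SAP is to be final before any analysis.

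Ischemia time enters a model only in section 11.8. There the ANCOVA for feasibility measures may "also take the site and the time from onset of AMI symptoms to PCI as covariates in the ANCOVA model", and the CMH test is controlled for it.

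**The concern.** Whether the treatment effect varies with ischemia time is a question about a difference between effects. A subset analysis gives one effect per subset. Finding one band significant and another not does not show that the two effects differ, and the plan contains no step that compares them. The covariate in section 11.8 does not fill the gap. A main effect of time adjusts the outcome for time, but it says nothing about whether treatment works better early or late.

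The groupings also overlap. The over 6 to 12 hour band appears in both, and the up to 6 hour group is the union of the first two bands. That leaves four distinct subsets, some of them probably small.

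At stake is how an exploratory Phase 2 result is read. A chance pattern across small subsets could be taken as evidence about which patients benefit.

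**Working it through.** **Inputs.** Effect 10.0 ml, SD 14 ml, two-sided 5%, power 80%, dropout about 4%, N = 105 at 1:1:1 (section 11.5); nominal 0.05 for all tests (section 11.2); bands from section 8.2. Stratum sizes are not given, so they are assumed and varied.

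**The plan's own sample size.** A two-sample t-test for 10 ml, SD 14, needs 31.8, so 32 per arm. Then 32/0.96 = 33.3, so 34 per arm and 102 in total. This is close to the stated 105, so the planning figures are used below at 33-35 per arm.

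**False positives with no true effect, one endpoint.** With k independent tests the chance of at least one p ≤ 0.05 is 1 − 0.95^k: 18.5% for k = 4, 26.5% for k = 6, 33.7% for k = 8. The tests here are correlated, because the doses share a placebo group and the 6-hour group contains two of the bands. The rates were therefore simulated (1,000,000 runs with known variance, 100,000 with t-tests) over seven splits from 5/75/20% to equal thirds. The repeated late band was counted once.

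| Tests assumed | Distinct tests | Chance of at least one p ≤ 0.05 |
|---|---|---|
| Each dose vs placebo, three bands | 6 | 24-25% |
| Each dose vs placebo, both groupings | 8 | 26.0-27.7% |
| Pooled MPC vs placebo, both groupings | 4 | 15.0-16.2% |
| One arm-by-band interaction F test (4 df) | 1 | 5.0-5.1% |

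**Mixed results when the effect is uniform.** Let a true 10 ml effect hold in every band, with within-band powers p1, p2, p3 from the two-sample t-test. For one dose the bands contain different subjects, so the tests are independent when each uses its own variance. The chance that some but not all three are significant is 1 − p1·p2·p3 − (1−p1)(1−p2)(1−p3).

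- 11/11/11 per arm: power 0.358 each; 1 − 0.046 − 0.265 = 69%.
- 12/12/11: powers 0.387, 0.387, 0.358; 1 − 0.054 − 0.241 = 71% (0.705).
- 7/20/7: powers 0.234, 0.595, 0.234; 1 − 0.033 − 0.238 = 73%.
- 4/20/10: powers 0.137, 0.595, 0.328; 1 − 0.027 − 0.235 = 74%.

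So the figure is about 70-75% over these splits. It reaches 78% at the very uneven 3/27/4 (powers 0.105, 0.731, 0.137; 1 − 0.011 − 0.208).

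**What an interaction can deliver.** Take two bands of 11 per arm. The difference between their effects for one dose has standard error 14·√(4/11) = 8.44 ml, so a 95% interval of about ± 1.96 × 8.44 = 16.5 ml. If the effects differed by 10 ml (an assumption), 10/8.44 = 1.18, and power is about Φ(1.18 − 1.96) = 22%. Baseline adjustment would improve this only as far as it lowers the SD below 14 ml.

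**The case against.** The strongest reply is that section 8.2 promises only subset analyses. These could be estimates with intervals, or a stratified or interaction model, and section 11.2 leaves further pre-specified hypotheses to a SAP that is to be finalized before analysis. This stands in part. A reader might infer that the plan has chosen separate significance tests of each dose in every subset. The text does not say so. That reading comes from combining the blanket 0.05 rule with the per-dose primary comparison, and the 26-28% depends on it. If only the pooled MPC group is compared, which section 11.2 allows under conditions, the figure is 15-16%.

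It is also fair that these analyses are exploratory. A reader might infer that a confirmatory claim is inflated. It is not, because section 4.2 speaks of exploring and section 11.2 labels the tests accordingly.

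Nor do the numbers support the idea that the subsets will nearly always disagree. With no effect, one dose tested in three bands gives a mixed picture in about 1 − 0.95³ = 14% of trials. The 70-75% arises only under a uniform true effect.

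Finally, the second grouping is not pointless. It merges two bands into a larger group, about 22 per arm under equal thirds, with about 64% power for 10 ml. Whether to keep it is a matter of preference.

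None of this supplies the missing comparison. In the text as it stands, no analysis addresses whether the effect changes with ischemia time.

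**Conclusion.** The concern holds as a gap in method, of modest weight. It rests on the absence of any treatment-by-ischemia-time term, which can be read directly from sections 8.2, 11.2 and 11.8 and depends on no assumption.

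The error rates illustrate the cost of filling the gap with per-subset significance. They are conditional on one endpoint, testing at nominal 0.05, normal outcomes and assumed stratum sizes, and more endpoints would raise them. The mixed-result figure further assumes the planning effect of 10 ml and SD of 14 ml in every band.

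**What to change.** State in sections 8.2 and 11.2 that effect modification by ischemia time is assessed by an arm-by-ischemia-time interaction in the LVESV ANCOVA, fitted with the main effect of time and kept separate from the primary model. Fix in advance whether time enters as hours or as the randomization bands; either would close the gap. Report the subset results as estimates with 95% intervals and say that they are descriptive.

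The cost is wording. Ischemia duration is already needed for stratification, so no subjects, visits or data are added. The downside is low power: a non-significant interaction will not show that the effect is constant, and the result will mostly be a wide interval.

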8.3 Clinical Endpoints

Clinical Endpoints will be assessed throughout the index hospitalization as well as at outpatient visits at 14 and 30 days, and at 3, 6, 12, 18 and 24 months after the index cardiac catheterization procedure, including:

- Occurrence of MACCE:
 - Cardiovascular death
 - Non-fatal myocardial infarction
 - Non-fatal stroke
 - Cardiac hospitalization due to heart failure
- Target vessel (or other vessel) revascularization post index cardiac catheterization and new or worsening heart failure during the index hospitalization will be tracked as “Adverse Events of Special Interest”.
- Total number of subjects with documented ventricular arrhythmia (sustained and non-sustained VT/VF) throughout the study period.
- Angina pectoris as defined by CCS clinical clarification.
- Functional status will be classified by the NYHA criteria.

9. ASSESSMENT OF SAFETY

9.1 Safety Endpoints

All safety endpoints will be assessed from subject randomization through up to 24 months post investigational agent infusion:

- SAE / AE rates
- Occurrence of MACCE including:
 - Cardiovascular death
 - Non-fatal myocardial infarction
 - Non-fatal stroke
 - Cardiac hospitalization due to heart failure
- Target vessel (or other vessel) revascularization post index cardiac catheterization and new or worsening heart failure during the index hospitalization will be tracked as “Adverse Events of Special Interest”.
- Total number of subjects with documented ventricular arrhythmia (sustained and non-sustained VT/VF) throughout the study period.
- Angina pectoris as defined by CCS clinical clarification.
- NYHA Class.
- Telemetry/48 hour Holter monitoring (during hospital admission and at 14 and 30 days, 3 and 6 months follow-up time points) with assessment of occurrence of ventricular arrhythmia.
- TIMI flow and perfusion measurements following intracoronary infusion of the MPC cell solution compared with placebo.
- Physical examinations, monitoring of vital signs (heart rate, respiratory rate, BP, and temperature).
- Results of clinical laboratory tests (hematology, serum chemistry, inflammatory markers), and immunogenicity assays; (flow cytometry Class I and Class II HLA percent reactivity % with specificity, antibovine and antimurine antibody analysis).

AE will be collected after a subject has been randomized. The AE will be graded according to the protocol as “mild”, “moderate”, “severe” and will be classified according to MedDRA.

An independent DSMB will review all safety and relevant clinical data at regular intervals in accordance with their charter. Based on its findings, the DSMB will make recommendations regarding study continuation, enrollment and/or study modification(s).

The primary safety analysis will be performed on the following safety and feasibility parameters up to 30 days post-treatment:

- TIMI flow prior to, during (approximately 50% of total infusion of investigational agent) and following infusion of investigational agent after successful PCI.
- SAE/AE rates.
- Results of clinical laboratory tests (including hematology, serum chemistry, inflammatory markers, flow cytometry anti-HLA Class I and Class II percent reactivity with specificity, antibovine and antimurine antibody analysis).
- Infusion procedure monitoring of vital signs (heart rate, respiratory rate, BP, and temperature).

9.2 Adverse Events

Each AE should be assessed by the investigator to establish its seriousness, severity and causality (relationship to the investigational product).

